5.7 Follow-Up

After End of Treatment assessments, all participants will enter follow-up for a maximum of 5 years. This is comprised of:

- **Response Follow-up-** for those who have yet progress
- **Long-term Follow-up-** for all participants who have progressed OR completed Response Follow-Up for survival and long-term toxicities. This follow-up will be performed typically via medical record review.

Assessment time points and windows are detailed in [Section 11.0](#).

5.8 Duration of Study Participation

The reason(s) for discontinuing study participation should be documented and may include:

- Completion of study activities (treatment and follow-up)
- Withdrawal of consent (See [Section 17.5](#))
- Participant is lost to follow-up. All attempts to contact the participant must be documented.
- At the discretion of the investigator for safety, behavioral, study termination or administrative reasons

The reason for study completion and associated date must be documented in the source documentation and the study-specific case report form (CRF). The participant's status is to be modified in the COH CTMS once the participant completes the study.

5.9 Supportive Care, Prohibited Medications and Concomitant Therapy

If concomitant therapy must be added or changed, including over-the-counter medications or alternative therapies, the reason and name of the agent/therapy should be reported in the eCRF and recorded in the EHR.

5.9.1 Prohibited Therapy

The following therapies are prohibited from **Cycle 1 Day 1 until completion of End of Treatment visit procedures**.

- Other investigational therapy/agent
- Other anticancer agents
- Antiandrogen agents (bicalutamide, flutamide)
- EXCEPTION: patients that enrolled on the study with asymptomatic low volume locoregional recurrent disease which was not amenable to SBRT at the time of enrollment will be followed with re-imaging scans. They will be reassessed at later time points during the study for further local control if needed.

5.9.2 Supportive Care

With the exception of prohibited therapies (see [Section 5.9.1](#)), participants should receive prophylactic or supportive care as clinically indicated per institutional policies.

Treatment /prevention of osteoporosis

- Treatment with bisphosphonates or RANK Ligand inhibitors (e.g. denosumab) is required
- Calcium supplementation, Vitamin D are also highly encouraged.
- For the treatment /prevention of osteoporosis doses and schedule must be consistent with the treatment or prevention of osteoporosis.

Non-pathological fractures

- If in weight-bearing bones follow dose delay guidelines in [Section 6.3](#).

Pathological fractures

- Pathological fractures may occur as the result of either progressive disease or increased physical activity associated with significant pain palliation.
- Treat in a manner that attempts to maintain the best functional status and quality of life.

Erythropoietin-stimulating factors, granulocyte colony stimulating factors

- Allowed

Prophylactic treatment for gastrointestinal AEs

- Prophylactic treatment for nausea and vomiting not recommended; however, anti-emetic drugs may be used when needed.
 - Laxative can be continued as concomitant medication, but start of prophylactic treatments before radium Ra 223 dichloride injection is not recommended. Laxative may be used when needed.
- No prophylactic treatment for diarrhea is recommended.

Surgery

- If surgery is required, the patient should continue with study treatment, if this is considered safe in the treating Investigator's opinion. The surgeon needs to be notified that the patient has been given radioactive drug, and needs to follow the guidelines for radioactive protection.

6.0 CRITERIA FOR INITIATING SBRT AND RADIUM RA 223 DICHLORIDE & DOSE DELAY GUIDELINES

6.1 Criteria to START SBRT (Cycle 1 Day 1)

Table 6.1 details criteria participants must meet to initiate SBRT.

Table 6.1 Cycle 1 Day 1 SBRT Administration Criteria

Criteria to be met in order to START SBRT	Action if criterion to the RIGHT is NOT met
1. ANC $\geq 1,500/\text{mm}^3$ NOTE: Growth factor support is not permitted to normalize baseline ANC parameters, however subsequent growth factor administration is permitted as standard supportive care.	Permanently discontinue protocol therapy if unable to initiate SBRT 28 (+ 7) days post-1 st dose of ADT (time constraint exception is in patients who started ADT concurrent with radiation tx or surgery). ADT may continue as a non-protocol therapy if clinically indicated.
2. Platelets $\geq 100,000/\text{mm}^3$ *	
3. Hgb $\geq 9.0 \text{ g/dL}$ *	
*NOTE: Transfusion of blood products are not allowed to normalize baseline blood parameters, however subsequent transfusions are allowed per standard supportive care guidelines.	
4. Not experienced \geq recurrent Grade 3 ADT-related AE	Permanently discontinue protocol therapy.
5. ADT related AEs \leq Grade 2	Permanently discontinue protocol therapy if unable to initiate SBRT 28 (+7) days post-1 st dose of ADT (time constraint exception is in patients who started ADT concurrent with radiation tx or surgery). ADT may continue as non-protocol therapy if clinically indicated.
6. Absence of toxicity not present at baseline that might adversely affect participation or results in a reasonable delay prior to initiating SBRT	Permanently discontinue protocol therapy. ADT may continue as non-protocol therapy if clinically indicated.

6.2 Criteria to START Radium Ra 223 Dichloride (Cycle 2 Day 1)

Table 6.2 details criteria participants must meet to initiate radium Ra 223 dichloride therapy.

Table 6.2 Cycle 2 Day 1 Radium Ra 223 Dichloride START Criteria

Criteria to be met in order to START 1 st dose of radium Ra 223 dichloride	Action if criterion to the RIGHT is NOT met
1. ANC \geq 1,500/mm ³ NOTE: Growth factor support is not permitted to normalize baseline ANC parameters, however subsequent growth factor administration is permitted as standard supportive care.	Delay initiating radium Ra 223 dichloride until criterion is met. Permanently discontinue radium Ra 223 dichloride if unable to initiate within 28 days of planned dose.
2. Platelets \geq 100,000/mm ³ *	
3. Hgb \geq 9.0 g/dL *	
* NOTE: Transfusion of blood products are not allowed to normalize baseline blood parameters, however subsequent transfusions are allowed per standard supportive care guidelines	
4. Not experienced \geq recurrent Grade 3 treatment-related AE	Permanently discontinue protocol therapy.
5. Treatment related AEs \leq Grade 2	Delay initiating radium Ra 223 dichloride until resolution of treatment-related AE to \leq Grade 2. Permanently discontinue radium Ra 223 dichloride if unable to initiate within 28 days of planned dose.
6. Absence of unrelated toxicity not present at baseline that might adversely affect participation or results in a reasonable delay prior to initiating radium Ra 223 dichloride	Permanently discontinue radium Ra 223 dichloride OR Delay initiating until criterion is met; permanently discontinue radium Ra 223 dichloride if unable to initiate within 28 days of planned dose.

6.3 Dose Delay Guidelines

- Toxicities will be graded using the NCI [CTCAE v 5.0](#).
- Baseline values are from the last values obtained prior to treatment.
- If one agent is permanently discontinued, then the participant may continue with the other agent(s).
- **SBRT**
 - If there is concern of toxicity to critical normal structures the SBRT dose will be sculpted according to national guidelines to conform to limit risk of toxicities to normal structures to $\leq 5\%$.
 - If a participant does not complete the SBRT segment as planned, then that participant may receive the other study agent(s) as clinically indicated.
- **Radium Ra 223 dichloride and ADT**
 - Only dose delays are permitted
 - See [Table 6.3](#) for dose delay guidelines
 - Participants may continue to receive ADT as clinically indicated and per investigator discretion if radium Ra 223 dichloride is discontinued.

Table 6.3 Dose Delay Guidelines

Toxicity	Agent most likely attributed to toxicity	Treatment Delay Guidelines
Hematologic		
Neutropenia (ANC) Grade 3/4 G3: 500- <1000/mm ³ G4: <500/mm ³	Radium Ra 223 Dichloride	First occurrence 
 • Hold the planned dose • Resume when toxicity resolves to \leq Grade 2 AND > 14 days have passed from growth factor support discontinuation • Permanently discontinue study agent if the planned dose is delayed > 28 days. Second occurrence 
 • Permanently discontinue study agent.
Febrile neutropenia Grade 3/4 G3: ANC <1000/mm ³ with a single temperature of >38.3 degrees C (101 degrees F) or a sustained temperature of ≥ 38 degrees C (100.4 degrees F) for more than one hour. G4: Life-threatening consequences; urgent intervention indicated	Radium Ra 223 Dichloride	First occurrence 
 • Hold the planned dose • Resume when ANC resolves to \leq Grade 2 AND > 14 days have passed from growth factor support discontinuation • Permanently discontinue study agent if the planned dose is delayed > 28 days. Second occurrence 
 • Permanently discontinue study agent.

Toxicity	Agent most likely attributed to toxicity	Treatment Delay Guidelines
Thrombocytopenia Grade 3/4 G3: 25,000-<50,000/mm ³ G4: <25,000/mm ³	Radium Ra 223 Dichloride	First occurrence 
 Hold the planned dose Resume when toxicity resolves to ≤ Grade 2 AND 14 days have passed from last platelet transfusion Permanently discontinue study agent if the planned dose is delayed >28 days. Second occurrence 
 Permanently discontinue study agent.
Other Non-hematological toxicities		
≥ Grade 3	Leuprolide Goserelin Degarelix Relugolix	First occurrence 
 Hold next planned dose until toxicity resolves to ≤ Grade 2. Permanently discontinue ADT if the planned dose is delayed > 42 days. 
 Exception: if testosterone level remains in the castrated state (<50 ng/dL), then participant can remain on the study following consultation with the Study PI or designee. Second occurrence 
 Permanently discontinue protocol therapy.
≥ Grade 3	Radium Ra 223 Dichloride	First occurrence 
 Hold next planned dose until toxicity resolves to ≤ Grade 2. Permanently discontinue study agent if the planned dose is delayed > 28 days. Second occurrence 
 Permanently discontinue protocol therapy.
Non-hematological toxicities- UNRELATED		
Any Grade	UNRELATED	
 Maintain treatment with study agent/ regimen. Interruption of protocol therapy is permitted if the investigator consults with the Study PI to determine that this is in the best interest of the participant.

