- **Unrelated** -The AE is clearly not related to the investigational agent or study procedure and is attributable to another cause(s).

Deviations and Unanticipated Problems

Deviation - A deviation is a divergence from a specific element of a protocol that occurred without prior IRB approval. Investigators may deviate from the protocol to eliminate immediate hazard(s) for the protection, safety, and well-being of the study subjects without prior IRB approval. For any such deviation, the PI will notify the COH DSMC and IRB within 5 calendar days of its occurrence via [iRIS](#) in accordance with the [Clinical Research Protocol Deviation policy](#).

Single Subject Exception (SSE)

An SSE is a planned deviation, meaning that it involves circumstances in which the specific procedures called for in a protocol are not in the best interests of a specific patient. It is a deviation that is anticipated and receives prior approval by the PI and the IRB. The SSE must be submitted as a "Single Subject Exception Amendment Request" via [iRIS](#) in accordance with IRB guidelines and the [Clinical Research Protocol Deviation policy](#). An IRB approved SSE does not need to be submitted as a deviation to the DSMC.

Unanticipated Problem (UP) – Any incident, experience, or outcome that **meets all three** of the following criteria:

1. Unexpected (in terms of nature, severity, or frequency) given the following: a) the research procedures described in the protocol-related documents such as the IRB approved research protocol, informed consent document or Investigator Brochure (IB); and b) the characteristics of the subject population being studied; **AND**
2. Related or possibly related to participation in the research (possibly related means there is a reasonable possibility that the incident, experience, or outcomes may have been caused by the drugs, devices or procedures involved in the research); **AND**
3. Suggests that the research places subjects or others at greater risk of harm (including physical, psychological, economic, or social harm) than previously known or recognized.

Any UP that occurs during study conduct will be reported to the DSMC and IRB in accordance with the [City of Hope's Institutional policy](#) using iRIS.

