13.0 STATISTICAL CONSIDERATIONS

13.1 Study Design

This multimodality Phase2study is designed to test the preliminary efficacy and to determine if androgen deprivation therapy (ADT), stereotactic body radiation therapy (SBRT) and radium Ra 223 dichloride, all delivered at the standard doses are well-tolerated in patients with oligometastatic hormone sensitive prostate cancer. The motivation behind using the standard doses for each as the starting dose is due to the limited sites of SBRT permitted in this study (≤ 4 metastatic lesion) and the prior data of radium Ra 223 dichloride when combined with ADT in a more advanced disease setting which suggest that the standard dosing should be safe and appropriate[21].

Correlative tissue studies are also incorporated into this protocol to explore the prevalence of genomic alterations in this population. Additionally, changes in immune biomarkers over the course of ADT-radiotherapy will be analyzed in an exploratory manner.

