13.4 Stopping Rules for Excessive Toxicity

The stopping rules for safety/toxicity will be assessed for each patient after the first 2 cycles of radium dichloride 223. The expected rate of unacceptable toxicity should not be $\geq 33\%$.

A patient will be deemed to have experienced an Unacceptable Toxicity (UT) if any of the following occur during the **first 2 cycles of radium Ra 223 dichloride (Cycles 2 and 3)** and are attributed as possibly, probably, or definitely related to protocol therapy:

- **Hematological**
 - Any \geq Grade 3 hematological toxicity that delays the next planned dose of radium Ra 223 dichloride by > 28 days

○ *Non-hematological*

- Any >Grade 2 fracture
- Any \geq Grade 3 non-hematological toxicity that does not resolve to \leq Grade 2 with adequate supportive care and delays the next planned dose of radium Ra 223 dichloride by > 28 days
- Any recurrent \geq Grade 3 toxicity

The following table will be consulted as relevant toxicities defined above are encountered.

When a stopping rule is triggered, the study PMT will review and assess the safety of the trial and submit a report to the COH DSMC. The COH DSMC will review for approval any decision to continue accrual, amend the protocol, or permanently suspend accrual to the trial.

# of patients treated that determines early stopping	# of patients with unacceptable toxicity	Given the following toxicity rates, cumulative probability of early stopping:		
		10%	25%	35%
≤ 6	2	0.11	0.47	0.68
≤ 10	3	0.14	0.56	0.80
≤ 12	4	0.14	0.58	0.81
≤ 15	5	0.14	0.59	0.83
≤ 18	6	0.14	0.60	0.85
≤ 21	7	0.14	0.61	0.86
< 24	8	0.14	0.61	0.86

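### A first, lasting, non-fracture Grade 3 or higher non-hematological event attributed to ADT or SBRT enters the stopping rule only if radium happens to be delayed, which Table 6.3 does not call for

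*Combined protocol and SAP*

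**What the plan says.** - **Scope (13.4).** Events count as unacceptable toxicity if they occur in the first two radium cycles (Cycles 2 and 3) and "are attributed as possibly, probably, or definitely related to protocol therapy". ADT and SBRT events are therefore in scope. Section 13.1 frames the question in the same way: whether the three treatments, "all delivered at the standard doses are well-tolerated in patients with oligometastatic hormone sensitive prostate cancer".
- **Non-hematological limbs (13.4).** There are three: a fracture above Grade 2; a Grade 3 or higher event that does not resolve to Grade 2 or lower "with adequate supportive care and delays the next planned dose of radium Ra 223 dichloride by > 28 days"; and a recurrent Grade 3 or higher toxicity. Only the second needs a radium delay.
- **Management after the first radium dose (6.3, Table 6.3).** Rows are set by the agent most likely responsible. The radium row holds radium, with a 28-day limit. The ADT row holds the next planned dose and then says "Permanently discontinue ADT if the planned dose is delayed > 42 days"; a second occurrence ends all protocol therapy. SBRT has no row. Section 6.3 also lets a participant who permanently stops one agent continue the others.
- **Management before the first radium dose (6.2, Table 6.2).** For a treatment-related event above Grade 2 the instruction is "Delay initiating radium Ra 223 dichloride until resolution of treatment-related AE" to Grade 2 or lower, whichever agent is responsible.

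**The concern.** The persistent-toxicity limb uses a radium delay as its marker of severity. That works for events managed by holding radium. It works poorly for events whose stated management leaves radium on schedule.

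Take a man with a single severe ADT-attributed event in Cycle 2 that never resolves. Under 6.3 he may lose ADT permanently and still receive radium on time. Or take a man with lasting radiation myelitis, which 7.5 lists as a possible and sometimes permanent SBRT injury. If the plan is followed as written and neither man has a fracture or a recurrence, neither counts. A man with a 29-day radium delay from an unresolved related Grade 3 event does count.

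At stake is whether the printed early-stopping probabilities describe the toxicity that 13.4 says it monitors. Events lost in this way lower the counted rate, and so the chance that the rule prompts a safety review.

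**Working it through.** **1. Where the gap lies**

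| Type of event | Is a radium hold stated? | Counts under 13.4? |
|---|---|---|
| Treatment-related, above Grade 2, before the first radium dose | Yes, any agent (Table 6.2) | Outside the window: under 5.2, Cycle 2 Day 1 is the day radium is given |
| Cycles 2-3, first, Grade 3+, attributed to radium | Yes (Table 6.3) | Yes, if unresolved and radium is delayed > 28 days |
| Cycles 2-3, first, Grade 3+, attributed to ADT | None stated; limit written for ADT | Only if radium happens to be delayed > 28 days |
| Cycles 2-3, first, Grade 3+, attributed to SBRT | No row | Only if radium happens to be delayed > 28 days |
| Fracture above Grade 2, at least possibly related to any protocol agent | Not needed | Yes |
| Recurrent Grade 3+, at least possibly related to any protocol agent | Not needed | Yes |

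Rows two to four refer to non-hematological, non-fracture events. The hold that ignores which agent is responsible ends where the monitoring window begins. The gap is rows three and four.

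**2. Reproducing the plan's table**

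Inputs from 13.4: stop at 2 events in up to 6 patients, 3 in up to 10, 4 in up to 12, 5 in up to 15, 6 in up to 18, 7 in up to 21, and 8 in fewer than 24.

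Let p be the counted rate, r(n) the boundary at patient n, and S(n,k) the probability of k events after n patients without having stopped. Then

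S(n,k) = S(n-1,k)(1-p) + S(n-1,k-1)p for k < r(n),

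and any probability that reaches r(n) is added to the stopping probability.

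First row at p = 0.10: 1 - 0.9^6 - 6(0.1)(0.9^5) = 1 - 0.5314 - 0.3543 = 0.114, printed as 0.11.

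Final row, with the last boundary applied through patient 23:

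| True rate | Printed | Computed |
|---|---|---|
| 10% | 0.14 | 0.138 |
| 25% | 0.61 | 0.618 |
| 35% | 0.86 | 0.866 |

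Applying the last boundary at patient 24 gives 0.138, 0.623 and 0.873. The printed table is sound if every qualifying event is counted.

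**3. Sensitivity to lost events**

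The documents give no share f of true unacceptable toxicities lost through the gap, so f is assumed. Counted rate = 0.35 × (1 - f).

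| Assumed f | Counted rate | P(early stop) |
|---|---|---|
| 0 | 0.350 | 0.87 |
| 5% | 0.3325 | 0.83 |
| 10% | 0.315 | 0.80 |
| 20% | 0.280 | 0.71 |

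**4. The price of counting more**

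With unchanged boundaries, the probability of a trigger is 0.14 at a counted rate of 10%, 0.21 at 12.5% and 0.28 at 15%.

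**The case against.** Much can be said for the plan as it stands.

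- **Purpose.** The secondary safety objective (1.2) is the safety of adding radium to SBRT and ADT, and ADT is standard of care. Tying unacceptable toxicity to whether radium can be delivered fits that aim. But 13.4 sets the wider scope, and its fracture and recurrence limbs do not depend on the agent.
- **Discretion.** Section 6.3 is guidance, the ADT row does not name which dose is held, 5.6 allows removal for a change in the participant's condition, and safety assessments are reviewed before each cycle. Radium could well be delayed in practice. That stands, but counting then rests on an unprescribed decision rather than on grade and duration. Table 6.3's explicit discretionary interruption is in the row for unrelated events, which cannot count.
- **Few events exposed.** Table 6.3 assigns every hematological row to radium. ADT events must be Grade 2 or lower before SBRT starts, and all treatment-related events must be so before radium starts. This stands, and it is why large lost shares should not be assumed.
- **Other oversight.** ADT and SBRT events still reach the protocol team and the DSMC through adverse event reporting. This also stands; the gap is in the formal rule only.

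A reader might infer more than the documents support:

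- *That such events can never count.* Fractures above Grade 2, recurrences and discretionary radium delays beyond 28 days all count.
- *That the gap explains why a regimen with 25-35% toxicity could reach 24 men without a trigger.* With every event counted, that already happens with probability of about 0.38 at 25% and 0.13 at 35%. Moreover, 25% is below the stated 33% limit.
- *That the attribution scale in 8.1 narrows the count.* It refers to the investigational agent or study procedure, and the latter can include SBRT; 13.4 sets its own scope.

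**Conclusion.** The concern holds in a narrow form. Section 13.4 claims to cover all protocol therapy, but for one class of event (first occurrence, unresolved, non-fracture, Grade 3 or higher, non-hematological, attributed mainly to ADT or SBRT, in Cycles 2-3) counting depends on a radium delay that Table 6.3 does not prescribe.

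The size cannot be fixed from the documents. Under assumed losses of 5% to 20% of true unacceptable toxicities, early stopping at a true 35% rate falls from 0.87 to between 0.83 and 0.71. The share is applied to the whole rate although only part of one limb is exposed, so the smaller values are the more cautious guide. The boundaries and the printed probabilities need no correction. The change is worth making because it lets the rule match its stated scope at modest cost.

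**What to change.** Change only what is counted. In the second non-hematological limb of 13.4, keep the radium-delay condition and add an alternative such as: *or, for an event at least possibly related to SBRT or protocol ADT, does not resolve to Grade 2 or lower within 28 days despite adequate supportive care*. Leave the boundaries as they are.

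Separately, the sponsor should reconcile Tables 6.2 and 6.3 with 13.4, since they treat the same kind of event differently before and after the first radium dose. No hold rule is proposed here.

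Cost: a protocol wording amendment, and enough data to establish when an event resolved (12.2 specifies the highest grade per cycle, which alone would not show this). More events would count, so triggers become more likely. If the counted rate rose from 10% to 12.5% or 15% (assumed), the trigger probability would rise from 0.14 to 0.21 or 0.28. Under 13.4 a trigger leads to review by the protocol team and the DSMC, not to automatic closure.
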